8. POTENTIAL BENEFITS

Participants may benefit from the comprehensive diagnostic assessment provided at the outset of the study. Patients with RNT may also benefit by experiencing relief from their symptoms. For participants assigned to AR-ERT, this treatment includes elements that have been shown to lead to decreased symptomatology in mood and anxiety disorders, and to improve quality of life and functional impairment. For participants assigned to SPT, this therapy is commonly offered by community clinicians for affective disorders, and thus is comparable to services patients might receive elsewhere. SPT is also acceptable from a safety perspective, as it allows for close monitoring.

Indirect benefits of the study include increased knowledge regarding treatment for RNT that will improve interventions for future patients and decreased impact of psychiatric illnesses characterized by RNT on society (i.e., reduced health care costs and disability). The knowledge to be gained by the proposed research has enormous public health importance because RNT is highly prevalent in the general population, and excessive healthcare costs are being spent on treatments that are not optimally effective. Mood and anxiety disorders are among the most common and disabling mental health conditions world-wide, and given their high comorbidity, prioritizing the understanding and treatment of shared characteristics like RNT may lead to more efficacious interventions for a broader range of patients. Although cognitive behavioral therapy is considered an effective first line intervention, many patients receiving this treatment are deemed non-responders, suggesting that underlying factors – such as RNT, which remains a residual symptom – are not being fully addressed. Thus, by engaging biobehavioral targets of attentional/cognitive control posited to underlie RNT and measuring target engagement and validation of this mechanism with a multi-method approach (i.e., ERPs, eye tracking), this study has great potential to improve the precision of RNT and emotion-focused therapies for affective disorders.

The risks that this study poses to participants are reasonable in relation to the importance of knowledge that may be expected to result because psychiatric disorders characterized by RNT are common, can be severe, and are often chronic. Thus, risks of discomfort associated with treatment are offset by the potential benefit of reduction of symptoms and improvement in mood, functioning, and quality of life for these patients. As such, the benefits of this study far outweigh the potential risks.

9. MONITORING AND QUALITY ASSURANCE

Therapist Training and Supervision

All treatment will be provided by masters- or doctoral-level mental health professionals experienced in cognitive behavioral techniques like AR-ERT, experienced in SPT, and familiar with affective disorders. We carefully considered the advantages and disadvantages of therapists providing one treatment but not the other (nesting within conditions) versus providing both treatments (crossing therapists with conditions).¹⁴² To assure equivalence of therapist training and competence, study therapists will provide therapy to patients in both conditions (AR-ERT and SPT).

Therapists will receive rigorous training before treating study patients. First, therapists will read the treatment manuals, related reading materials on AR-ERT and SPT, and readings on RNT. Therapists will then have to pass (i.e., 90% correct) a knowledge test about their

reading material. Therapists will attend a training led by [name] that consists of: (1) a discussion of the phenomenology and other important aspects of RNT, (2) an overview of implementation of the study protocol, (3) training on the manualized treatments, which will include slide presentations, role plays, and discussion, and (4) a discussion of the distinctiveness of the two treatments. To ensure ongoing high-quality treatment, therapists in each condition will receive weekly supervision from the PI ([name]) in AR-ERT and SPT. Care will be taken in supervision to ensure that specific AR-ERT techniques are not introduced into SPT.

Monitoring of Treatment Fidelity

All treatment sessions will be digitally audio recorded. A doctoral-level independent adherence rater will rate 5% of randomly selected sessions at regular intervals during the study using our adherence and competence measures described above. This will be done to ensure adherence to the treatment manuals (to minimize the risk that techniques implemented in AR-ERT are delivered in the SPT condition; i.e., therapist drift), consistency of treatment delivery, and competent delivery of the treatments. The adherence rater will have experience with both AR-ERT and SPT and will be further trained and supervised by [name]. He/she will attend the initial therapist training activities described above and will watch the training tapes of AR-ERT and SPT. Descriptive statistics on adherence and competence ratings will be obtained.

Independent Evaluator (IE) Qualifications and Ensuring IE Blindness

A blinded evaluation of outcomes by an IE is essential to obtain unbiased information on treatment efficacy. IEs will have a masters or doctoral degree in psychology or a related mental health field. We will take many steps to ensure that IEs remain blind to treatment condition throughout the study for all participants. IEs will not be told the treatment assignment for any participant. IEs will be trained to focus on outcome measurement only and to avoid any discussion of what treatment subjects are receiving. Moreover, patients will be reminded at each IE assessment not to discuss their treatment with the IE. Therapists and study staff will be regularly reminded of this as well. Supervisory discussions about treatment will occur in separate meetings attended only by therapists and supervising clinicians. Treatment and assessment recordings will be kept in separate locations. Furthermore, the IE will be asked to guess the treatment condition of each participant after the completion of the follow-up assessments or, for dropouts, after the last treatment session.

Establishing and Monitoring Interrater Reliability

The study team has extensive experience with the measures used in this study. Training and reliability checks will be done to ensure that IEs conduct ratings in a uniform way. IEs will first receive instruction in the Y-BOCS, SIGH-A, SIGH-D, and CGI-I/S from [name] in an initial study start-up meeting. Subsequently, IEs will rate Y-BOCS, SIGH-A, SIGH-D, and CGI-I/S training tapes of interviews conducted by [name]. IEs will be certified when they reach reliability criteria with [name] for these measures (defined by ICCs $\geq .8$).

To maintain inter-rater reliability during the study and reduce rater drift, all assessments will be audio recorded. A senior member of the OCD Program's staff will review and rate 5% of randomly selected digitally recorded interviews at regular intervals during the study. If reliability with this rater falls below the above criteria, we will institute retraining procedures. [name] will also conduct weekly supervision meetings with IEs during which assessment interviews from the past week will be discussed. Any problems in interview content and diagnostic disagreements will be addressed during supervision. Reliability statistics will be included in our publications.

Research Team Meetings

In addition to the study start up meetings described above, the PI and clinical research assistant will meet weekly to discuss the study, including recruitment, new subjects to ensure inclusion/exclusion criteria are met, withdrawal of any subjects, any safety issues, and other topics.

Data and Safety Monitoring Board (DSMB)

In order to provide the most comprehensive protection of participants, we will establish a formal data and safety monitoring board (DSMB). The DSMB will be comprised of 3 members who have expertise in clinical trials, anxiety, mood, and OC spectrum disorders, are not affiliated in any other way with the proposed project, and do not have an affiliation with the MGH/Harvard Medical School. Board members will consist of:

- 1) [name]., Professor of Psychiatry and Behavioral Sciences, Baylor College of Medicine
- 2) [name]., Associate Professor in Clinical Psychology and Director of the Anxiety and Depression Research Center at Southern Methodist University
- 3) [name]. Associate Professor and Director OCD & Related Disorders Program, University of South Florida

All board members are very familiar with safety and ethical concerns related to human subjects in clinical research. The DSMB will meet twice per year (by conference call) to review the study's progress, enrollment, deidentified group-level data for differential rates in key outcomes, and adverse events. They will be responsible for monitoring rates of enrollment and study retention, patient safety, and data confidentiality and entry. The DSMB will provide guidance to the PI ([name]) who will then be responsible for executing the data and safety monitoring plan and complying with the reporting requirements. The PI will provide a summary of the DSMB report to the NIH on an annual basis as part of the progress report. The DSMB report will include participants' sociodemographic characteristics, expected versus actual recruitment rates, treatment retention rates, any quality assurance or regulatory issues that occurred during the past year, summary of adverse events, and any actions or changes with respect to the protocol. The DSMB report will include, when available, the results of analyses that have been conducted.

Adverse Events Reporting

Based on information from previous studies involving EEG, clinical assessment, and treatment, the following adverse events are expected, as described in the consent form and reviewed in detail above in Section 3C:

1. Becoming tired or uncomfortable answering assessments and questionnaires
2. Discomfort from scraping skin on the scalp during EEG procedures
3. Distress from the computerized images during the eye-tracking task
4. Temporary increase in anxiety or depression during treatment
5. Possible loss of privacy (e.g., due to contacting an emergency-contact or due to legal limits of confidentiality)

An IRB approved AE Tracking log will be administered by the RA and reviewed by the PI at the clinical assessment visits (baseline, mid-treatment, post-treatment, and 3-month follow-up) to probe for any adverse events that occurred since the last visit.

Adverse events and Unanticipated problems will be reported to the MGB IRB in accordance with its policy. Specifically, in accordance with guidelines of the Office for Human Research Protections (OHRP) and NIMH, reporting of adverse events will occur to (1) the MGH IRB, (2) the NIMH program officer, (3) OHRP, and (4) the DSMB as follows:

- 1) Unexpected **serious adverse events** (SAE) related to study participation (e.g., death, life threatening AE, suicide attempt, inpatient hospitalization) will be reported within **5 business days** of the study team first learning of a death and within **10 business days** of the study team becoming aware of a non-death SAE.
- 2) Any **other unanticipated problems** involving risks to subjects or others will be reported within **10 business days** of the study team becoming aware of the event.
- 3) All **adverse events** and SAEs that are deemed expected or unrelated to the study will be summarized in **twice-annual progress reports** for the DSMB and in **annual progress reports** for the NIMH and IRB.

Documentation to be submitted for reportable events will include:

- Identifying information for the research protocol (e.g., project title, investigator's name, and the grant/contract number)
- The date on which the event occurred and the date at which the PI became aware of the event
- A detailed description of the event and impact on the participant(s)
- A detailed description of the measures taken (including clinical) in response to the event (if any)
- Confirmation that the appropriate monitoring entities and regulatory bodies have been notified as needed
- A description of any changes to the protocol or other corrective actions that have been taken or are proposed in response to the event

Data Management

REDCap™ (Research Electronic Data Capture) is a free, secure, HIPAA-compliant web-based application hosted by the Partners HealthCare Research Computing, Enterprise Research Infrastructure & Services (ERIS) group. Vanderbilt University, with collaboration from a consortium of academic and non-profit institutional partners, has developed this software toolset and workflow methodology for electronic collection and management of research and clinical study data. Data collection projects rely on a study-specific data dictionary defined by members of the research team with planning assistance from Harvard Catalyst | The Harvard Clinical and Translational Science Center EDC Support Staff. The iterative development and testing process result in a well-planned data collection strategy for individual studies. Using REDCap, the research team can also design web-based surveys and engage potential respondents using a variety of notification methods. REDCap provides flexible features that can be used for a variety of research projects and provides an intuitive interface to enter data with real time validation (automated data type and range checks). The system offers easy data manipulation with audit trails, reports for monitoring and querying participant records, and an automated export mechanism to common statistical packages (SPSS, SAS, Stata, R/S-Plus).

Scales are completed securely via the internet by using any device with standard web access and browsers. Participants and/or research staff will enter scale responses directly into REDCap electronic assessment forms. Using 256 bit RSA Secure Socket Layer (SSL) encryption, approved users will be logged-in to machines using secured browsers behind the Partners Healthcare Systems IS corporate firewall. Staff will have a unique identifying key that will link them to the electronic study forms. This unique ID will be used in addition to a randomly

generated secure password that only the staff person will have. Thus, under supervision by staff, each subject will only have access to complete his/her own scales and will not be able to view data from any other subjects.

Responses entered by subjects will be transmitted to and stored in a secured database at MGH. This database will be configured in REDCap by the database administrator who will set up strict permissions to maintain confidentiality. [name] will assist with creating logical checks to identify data inconsistencies, omissions, and errors in real-time. Issues identified will trigger queries, and problems will be resolved promptly. Emails will be automatically sent to research assistants when scales are completed so any missing data can be examined. Data will be backed up automatically nightly and downloaded from REDCap into SPSS for analysis.

Data collected from two instruments will be stored outside of the REDCap™ system. Specifically, data collected at screening from the clinician-administered computerized SCID-5-RV (NetSCID-5) will be saved within the TeleSage, Inc. system. TeleSage, Inc. ensures the privacy and confidentiality of NetSCID data using a rigorous set of procedures. Each participant is associated with a unique NetSCID project and its affiliated organization, as well as a coded participant ID. All data are stored on a Secured Socket Layer (SSL) HIPAA-compliant web server, encrypted at rest and geo-redundant data backup on a separate HIPAA-compliant database. Data is downloaded in encrypted format by users via a secure data download page. In addition, participant responses on the BDI-II at the 3-month follow-up time-point will be stored electronically utilizing the Q-global software system by Pearson, Inc. All data will be coded using a corresponding participant ID and stored on Pearson's servers or those of its affiliates and/or authorized vendors and will only be accessible by authorized employees, agents and contractors of Pearson and its affiliates and authorized vendors.

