Concomitant Therapy (CTHER) Log: The RA will administer the CHER form at the clinical assessment visits (baseline, mid-treatment, post-treatment, and 3-month follow-up) and before each therapy session to probe for any changes in therapy that may have occurred since the last session. Changes in therapy are not allowed during the study. At each visit, the research coordinator will ask the subject whether they have started or stopped any mental health treatments such as counseling, therapy, or self-help programs to ensure that this does not occur without our knowledge. The therapist reviews the completed CHER Log before each therapy session.

Life Events Questionnaire: This form is administered by the RA and reviewed by the PI at the clinical assessment visits (baseline, mid-treatment, post-treatment, and 3-month follow-up) to assess whether any major life events occurred since the last assessment visit that might have had a psychological impact on the participant including: marriage, divorce or separation from spouse, death of a spouse/partner or other close family member, birth of a child, serious injury, diagnosis/progression of a medical illness or disease (e.g., COVID-19 exposure or diagnosis), loss/began new job.

Adverse Events (AE) Form and Log: The AE Form will be administered by the RA during clinical assessment visits (baseline, mid-treatment, post-treatment, and 3-month follow-up) and by the therapist during treatment sessions to probe for any adverse events. Should the participant report an adverse event, the RA or therapist will log this information in the AE log while speaking to the participant. If there are any safety concerns during a clinical assessment, the RA will inform the IE of the adverse event. The RA and therapist will document any adverse events that occur during the study and the PI will review each event during weekly study meetings to discuss relatedness to treatment, severity, and corrective actions. We have used these forms in prior NIH-funded psychotherapy studies.

Assessment of Treatment Credibility and Satisfaction:

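### Serious adverse events deemed unrelated or expected reach the DSMB only in the twice-yearly summary, unless reported as another unanticipated problem; sending every SAE on the existing clocks would be a cheap, optional improvement

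*Combined protocol and SAP*

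**What the plan says.** Section 9, Adverse Events Reporting, names four recipients (the IRB, the NIMH program officer, OHRP and the DSMB) and sets three routes.

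- **Item 1** covers SAEs that are unexpected and "related to study participation (e.g., death, life threatening AE, suicide attempt, inpatient hospitalization) will be reported within" 5 business days for a death and 10 business days for any other SAE.
- **Item 2** covers any other unanticipated problem "involving risks to subjects or others will be reported within" 10 business days.
- **Item 3** covers the rest. Adverse events and "SAEs that are deemed expected or unrelated to the study will be summarized in" reports that go to the DSMB twice a year and to NIMH and the IRB once a year.

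The same section lists five expected adverse events. None is a death, a suicide attempt or a hospitalization; one is a transient worsening of anxiety or depression during therapy.

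A detailed event file is specified under "Documentation to be submitted for reportable events will include". For the DSMB's own report, the DSMB subsection lists a "summary of adverse events, and any actions or changes with respect to the protocol". The board meets by conference call twice a year, and no ad hoc meeting is described.

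On relatedness, Section 5 (Adverse Events Form and Log) says that "the PI will review each event during weekly study meetings to discuss relatedness to treatment, severity, and corrective actions". Section 9 (Therapist Training and Supervision) says that "therapists in each condition will receive weekly supervision from the PI", in both treatments.

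**The concern.** The label given to an SAE decides how soon the independent board hears of it. In a psychotherapy trial that label can be uncertain: a suicide attempt or psychiatric admission may reflect the underlying illness, the treatment, or both. If such an event is called unrelated, or is argued to be a form of the expected temporary worsening, it moves from the expedited route to the periodic summary unless item 2 catches it. A death judged unrelated takes the same slow route.

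The one relatedness review that the document describes is internal and led by the PI, who supervises delivery of both therapies. No independent check of attribution between DSMB meetings is described, and the board's summary may carry less detail than the file prepared for a reportable event.

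What is at stake is the timeliness of an outside check on the attribution and on the team's response. No endpoint, estimate or analysis is involved.

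**Working it through.** The plan states no waiting time, so there is no figure of its own to reproduce. The wait follows from the reporting frequency.

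**Inputs from Section 9.** Two DSMB reports a year; expedited clocks of 5 business days (death) and 10 business days (other SAE).

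**Assumptions.** The two reports are evenly spaced, events are equally likely at any time between reports, a working week has 5 business days, and time spent preparing the summary is ignored. All waits run from when the team learns of the event.

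1. Longest wait on the summary route: (365.25 / 7) / 2 = 26.1 weeks.
2. Average wait on the summary route: 26.1 / 2 = 13.0 weeks.
3. Expedited clocks: 5 / 5 = 1 week (death); 10 / 5 = 2 weeks (other SAE).
4. Largest difference in notice: about 26 − 1 = 25 weeks (death) or 26 − 2 = 24 weeks (other SAE). Average difference for another SAE: about 13 − 2 = 11 weeks.

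**Sensitivity to spacing.** The document does not fix the spacing. If the longer interval were 7 or 8 months, the longest wait would be 30.4 or 34.8 weeks.

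**Other outside bodies.** Item 3 gives NIMH and the IRB annual summaries, about 52 weeks at most. The DSMB report is therefore the earliest scheduled outside notice of such an event. For scale, a participant's last assessment is at week 20 (Section 5, Overview), so participation could end before the board is told.

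**How many events.** The document gives no SAE rate. Assume that 1% to 5% of the 62 Phase II participants have an SAE and that 25% to 100% of those SAEs are deemed unrelated or expected. Events that would change route = 62 × SAE rate × share:

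| Case | Calculation | Events |
|---|---|---|
| Low | 62 × 0.01 × 0.25 | 0.16 |
| Middle | 62 × 0.05 × 0.50 | 1.55 |
| High | 62 × 0.05 × 1.00 | 3.1 |

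The whole trial would thus see a handful of such events at most, and perhaps none.

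**The case against.** The case for leaving the plan alone is substantial.

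- **The rule is deliberate.** Section 9 sets out tiered reporting and says that it follows OHRP and NIMH guidelines. The tiers are internally consistent. A reader might infer a breach of a reporting standard; nothing in the documents shows one.
- **Notice is not review.** A reader might infer that independent review comes 24 weeks late. The 10-business-day clock governs when a report is sent, and the plan promises no review before the next call even on the expedited route. The figures above are differences in notice only.
- **Item 2 is broad.** It does not require an event to be judged related to treatment, so it may catch doubtful cases. Item 1 itself names suicide attempt and hospitalization as examples. A reader might infer that such events would routinely be labelled unrelated. Section 7 says only that symptoms fluctuate and that suicidality occurs in affective disorders; it does not say how an event would be attributed.
- **The PI may not decide alone.** Section 5 describes a discussion led by the PI, not who makes the final attribution. It supports saying that the review is not independent. It does not support an inference of bias or sole control.
- **Care is not delayed.** Events are reviewed weekly, a clinician is on call at all hours, and withdrawal is agreed with the therapist and a further named person (Section 7).
- **Other documents are unseen.** The data and safety monitoring plan and the IRB's policy are mentioned but not reproduced, and either could provide for ad hoc calls or fuller detail. Nothing in the DSMB subsection bars the board from asking.
- **Few may benefit.** Section 7 (Informed Consent) shows that participants had already enrolled before a February 2022 change, so a prospective amendment may cover fewer than 62.

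Most of this stands, and it limits the point to an optional improvement. It does not remove the gap: item 3 as written still sends these SAEs to the board only in a summary, and unseen documents cannot be assumed to override it.

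**Conclusion.** The point holds as an optional improvement to a stated design choice. An SAE deemed unrelated or expected, and not reported under item 2, may reach the DSMB up to about 26 weeks after the team learns of it (about 13 on average), against 1 or 2 weeks on the clocks that the plan already uses. This rests on even spacing of the two yearly reports, which the document does not state. The event count, roughly 0.2 to 3.1 over the trial, rests wholly on assumed rates. The expected route is the less likely one, since no death, suicide attempt or admission is on the expected list and an event would have to be argued onto it.

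A reader might also infer that the board needs each affected participant's treatment arm. The documents do not support this: the DSMB subsection describes group-level data without identifiers, and disclosing individual allocation would be a separate change needing its own justification.

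**What to change.** Add to Section 9, Adverse Events Reporting:

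> Every SAE, regardless of relatedness or expectedness, will be sent to the DSMB within 5 business days (death) or 10 business days (other SAE) of the study team becoming aware of it, with the event documentation listed below and the attribution and reasons.

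Add to Section 9, Data and Safety Monitoring Board:

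> The DSMB may call an ad hoc review after any SAE report.

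The second sentence is needed because faster notice alone does not produce an earlier review. Leave the IRB, NIMH and OHRP routes, and the twice-yearly summary of non-serious events, as they are.

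**Effect.** The longest time to DSMB notice falls from about 26 weeks to about 1 week (death) or 2 weeks (other SAE).

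**Cost.** One protocol amendment, probably no more than about three extra reports to the existing three-member board (at an assumed SAE rate of up to 5%), and a call if the board asks for one. Some of the reports will concern events plainly unrelated to the study.
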